3.7.3 Tertiary/Exploratory Endpoints

3.7.3.1 Health Care Resource Utilization (HCRU)

- Location of care for StrataGraft application (e.g. inpatient hospital, outpatient/ambulatory hospital, clinic, etc.).
- Treatment used for all other non-study burn areas following excision and % total body surface area (TBSA) treated with each.
- Number and duration of operating room procedures required for study burn treatment.
- Length of hospital stay.
- Prescription drug given for pain control.
- Antibiotics given for outpatient use at discharge.
- Re-admission within 30 days after discharge.
- Whether a re-admission is planned.
- Length of hospital stay of re-admission.

The above endpoint variables will be summarized with the number of subjects (n), mean, standard deviation, median, minimum, and maximum for continuous variables and frequency and percentage of subjects in each category will be presented for discrete variables.

3.7.3.2 Exploratory Endpoints

 Calculated total area of autologous (donor) skin applied to Study Tx sites by Month 6

The cumulative total area of donor skin applied to both AG Tx and SOMA Tx sites will be summarized with number of subjects, mean, median, standard deviation, minimum, and maximum up to Month 6 by treatment sites, by relative autograft mesh ratio group at the SOMA Tx site (m+1 and m+2), and all subjects The calculated total donor area is determined by dividing the treatment area by the relevant total mesh ratio up to Month 6. If a subject undergoes re-grafting, the area of the donor site used for the re-graft is included in the total calculation. Calculation of the total mesh ratio is detailed in Section 3.7.1.

 Time to First Confirmed Complete Wound Closure Without Additional Autograft by Month 2

The event for the Kaplan-Meier method is defined as the first occurrence of confirmed complete wound closures without additional autograft by Month 2. The time to first complete wound closure by treatment site will be analyzed using the Kaplan-Meier estimation method. The time period for this analysis is calculated as (the date of the first event - the date of Day 1 + 1). Treatment sites that do not experience any event during the study will have their time censored at the last available date in the study.

The Kaplan-Meier estimate will be used to determine the median time to first confirmed complete wound closure without additional autograft by treatment site.

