Following excision, a total of 20 subjects (Cohort 1) will be randomized into one of 2 groups, Group 1 and Group 2.

Following completion of the Day 28 assessments, each subject will be determined to be a success or failure based upon the criteria below:

- % closed at Day 28, with success declared if the difference between paired wounds
 10%, and
- Total score of Observer assessment of the POSAS at Day 28, with success declared if the difference between paired wounds < 20%.

Group success will be declared if \geq 80% subjects are determined to have treatment success within that group. Only one of the 2 SOMA Txs, m+1 or m+2, will be determined to meet the *a priori* established criteria above and become the SOMA Tx in Cohort 2.

Treatment Groups and Duration:

This study is open-label. Subjects will serve as their own control. Subjects will be randomized to receive autograft, meshed at a ratio per clinician judgment at 1 treatment site (m), and StrataGraft overlay of autograft at either m+1 (i.e., group 1) or m+2 (group 2), relative to the control autograft mesh ratio.

It is anticipated that each subject will participate in this study for up to 14 months: up to 2 weeks of screening followed by up to 12 months (± 4 weeks) of post-treatment observation.

Estimated Duration of Study

Enrollment ~36 months.

Duration of subject participation up to 60 weeks.

Total study duration ~96 months.

Study Was Terminated Early by Sponsor

Study enrollment was terminated on 12 January 2024 due to a decision to voluntarily discontinue sale and manufacture of StrataGraft for business reasons. A total of 13 subjects were randomized, all in Cohort 1, at the time of termination of enrollment. Follow up for enrolled subjects was completed in April 2024.

Scientific Rationale for Study Design

The current standard of care for closure of FT burns is autografting, i.e., the surgical harvest of healthy skin from an uninjured site and subsequent transplantation of the donor tissue to the wound following surgical excision of nonviable tissue from the burn. While this method is effective in achieving closure of the original wound, optimal sites for the harvest of donor skin are often limited, and closure of large areas of injury may necessitate sequential re-harvest of available donor sites. Additionally, the donor site is painful, susceptible to infection and scarring,

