2.2.7 Modification from the Statistical Section of the Final Protocol

The amendments to the statistical section and relevant endpoints of the final protocol are displayed here. The final analyses are based on this final SAP. The amendments are as follows:

In protocol section 4, objectives and endpoints (p. 19):

The exploratory endpoint, "Effect of total wound burden on rate of wound closure," is listed. However, no data has been collected on overall donor site closures. Consequently, no analysis will be performed for this endpoint.

- The protocol does not mention the endpoint 'Time to First Confirmed Wound Closure
 Without Additional Autograft by Month 2.' (see Section 2.2.3) However, this endpoint and
 its results were outlined in the briefing document (see the References: Type B Meeting
 Briefing Materials submitted in IND 010113 Sequence 0151 on 27 November 2023),
 leading to its inclusion.
- In protocol section 10.3.2 Efficacy Analyses (p36):
 The original analyses for the first co-primary endpoint as stated in the clinical protocol were as follows:

For calculated percent reduction of donor skin (as defined by [1-(AG Tx mesh ratio/SOMA Tx mesh ratio) × 100]) at Month 2, the log-transformation of the endpoint will be performed, and geometric mean ratio percent reduction of donor skin between treatment site will be presented.

A mixed-effect model repeated measures method with covariates, including subject treatment site, mesh ratio on SOMA Tx site, and cohort will be used for this log-transformed primary endpoint.

If the mixed-effect model repeated measures model does not converge or violates the model assumptions, the paired t-test will be used. If parametric statistics models are not appropriate, the Wilcoxon signed-rank test will be performed.

The updated statistical analysis will not use log-transformation, to facilitate easier clinical interpretation. Additionally, the mixed-effect model for repeated measures will not be used due to the small number of subjects and the existence of only one cohort. To ensure robustness of the method, the non-parametric Wilcoxon signed-rank test, as originally planned last method, will be used (see Section 3.7.1).

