2.5 Ad-hoc Data Review

Due to slow enrollment, the sponsor performed a preliminary assessment of the efficacy and safety of the product in April 2023 to determine the appropriateness of amending the ongoing Phase 1/2a StrataSOMA clinical study to a seamless Phase 1/2/3 study design. To this end, the sponsor performed an ad-hoc data analysis for the first 10 subjects enrolled in Cohort 1 after 1st 10 subjects completed primary endpoints assessments. Results of this data review were included

in Sponsor Meeting Materials for a Type B meeting with FDA to discuss the proposed clinical study amendment.

The ad-hoc data review demonstrated that all of the first 10 subjects enrolled in the StrataSOMA study achieved confirmed complete wound closure by or before Month 2 without additional autografting on both SOMA and AG treatment sites, regardless of whether they were randomized to the m+1 or m+2 group (i.e., 100% of the SOMA treatment sites achieved confirmed complete wound closure by or before Month 2 without additional autografting).

Additionally, SOMA treatment decreased the amount of donor tissue required to close treated sites relative to the control AG treatment site by 35% and 57% for autograft mesh ratios m+1 and m+2, respectively, without sacrificing cosmetic outcomes, as evidenced by comparable POSAS scores at Months 2 and 3.

For safety, ad hoc analyses of TEAEs or SAEs for the first 10 patients through the data cutoff showed that most TEAEs and SAEs were typical of what is observed in burn wounds and during wound healing. The safety profile at the StrataGraft treatment sites was similar to that of the control treatment sites, and no new safety signals were identified.

For details of the ad-hoc analyses, see the Type B Meeting Briefing Materials submitted in IND 010113 Sequence 0151 on 27 November 2023 (see References).

This ad-hoc data analysis will not alter the screened significance level of the entire study.

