3.7 Efficacy Analysis

Efficacy analyses will be performed comparing the differences between treatments within subjects, where appropriate. Descriptive summaries will be reported by treatment site, relative autograft mesh ratio group at the SOMA Tx site (m+1 and m+2), cohort and all subjects.

For continuous variables, descriptive statistics will include the following: the number of patients reflected in the calculation (n), mean, median, standard deviation, minimum, and maximum.

For categorical or ordinal data, frequencies and percentages will be displayed for each category. The definition of primary and secondary endpoints is described in Section 2.2.1 and 2.2.2.

Safety assessments will include monitoring of TEAEs, vital signs, laboratory safety values, incidence of wound infection-related events, and potential immunologic responses to StrataGraft.

Confidential and Proprietary

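### Time to confirmed closure is planned only as two per-site Kaplan-Meier medians; the within-subject difference in days, with an interval, is never estimated.

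*SAP*

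**What the plan says.** The SAP describes a design in which each subject is his or her own control. Section 3.7 sets the general rule: "Efficacy analyses will be performed comparing the differences between treatments within subjects, where appropriate".

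For time to first confirmed closure without additional autograft by Month 2, section 3.7.3.2 says "The time to first complete wound closure by treatment site will be analyzed using the Kaplan-Meier estimation method", and then: "The Kaplan-Meier estimate will be used to determine the median time to first confirmed complete wound closure without additional autograft by treatment site". Sites without an event are handled by this rule: "Treatment sites that do not experience any event during the study will have their time censored at the last available date in the study". The section names no difference between sites, no interval for a difference, and no paired or clustered method. SAP section 6 adds that the abbreviated CSR will contain no figures, so the curves will not be shown either.

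SAP 2.2.7 explains where the endpoint came from. It begins "The protocol does not mention the endpoint" and gives the reason for inclusion: the endpoint and "its results were outlined in the briefing document". Section 2.2.3 lists it among the exploratory endpoints without that remark.

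Two facts set the scale. On numbers, SAP 2.1 reports: "A total of 13 subjects were randomized, all in Cohort 1, at the time of termination of enrollment". On outcome, SAP 2.5 reports that "all of the first 10 subjects enrolled in the StrataSOMA study achieved confirmed complete wound closure by or before Month 2 without additional autografting", and that this was so at both the SOMA and the AG sites.

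**The concern.** The trial asks whether a more widely meshed autograft under StrataGraft closes as well as the control graft on the same patient. How much later the SOMA site closes, if at all, is a natural way to express the cost of the wider mesh. With 13 subjects, pairing is the main source of precision.

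Elsewhere the SAP uses the pairing wherever it gives a between-site p-value: McNemar for Month 2 closure (3.7.1), and paired t-tests for percent re-epithelialization and for the POSAS total score (3.7.2). Time to closure is the exception, and no reason is given. Two medians side by side do not estimate the typical within-subject delay and carry no statement of uncertainty about it. If they came out close, a reader could take that as evidence of no delay, when the data had not been analysed in a way that could show one. The stake is a missing estimate in a small exploratory data set. All p-values in this SAP are for signal screening, so no confirmatory claim is at risk.

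**Working it through.** The documents contain no power, precision or sample-size calculation for this endpoint, so there is no figure to reproduce.

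**1. What the Month 2 co-primary can show.** Inputs: 13 subjects (SAP 2.1), the first 10 closed at both sites (SAP 2.5). Discordant pairs possible: at most 13 − 10 = 3. Smallest two-sided exact McNemar p, with all 3 in one direction: 2 × 0.5³ = 0.25. With 10/10 at both sites the observed difference is 0, and the exact 95% lower bound per site is 0.025^(1/10) = 69.2% (0.025^(1/13) = 75.3% if 13/13). This endpoint cannot separate the sites.

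**2. What can be computed for time.** For those 10 subjects both sites have a confirmed closure by Month 2, so at least 10 differences in days come from subtraction, with no censoring. The Kaplan-Meier analysis already needs the same dates.

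**3. What pairing is worth.** SD and correlation r are not in the documents; both are assumed here. For the mean difference with n = 13:
- paired SE = SD × √(2(1 − r)/n), t on 12 df = 2.179
- independent-sites SE = SD × √(2/n), t on 24 df = 2.064
- ratio of SEs = √(1 − r): 0.71 at r = 0.5, 0.45 at r = 0.8, and 1 at r = 0

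At SD 8, r = 0.5: SE = 8 × √(1/13) = 2.22, full width 2 × 2.179 × 2.22 = 9.7 days. At r = 0.8: SE = 1.40, width 6.1. Independent: SE = 3.14, width 13.0. Simulated mean widths are slightly smaller, because the SD is estimated: 9.5, 6.0 and 12.8 days. Simulated signed-rank power for a true 5-day SOMA delay is about 0.52 at r = 0.5 and 0.88 at r = 0.8.

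Over a wider range of assumptions, 95% half-widths in days:

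| SD | r = 0.3 | r = 0.5 | r = 0.7 | r = 0.9 | independent |
|---|---|---|---|---|---|
| 7 | 5.0 | 4.2 | 3.3 | 1.9 | 5.7 |
| 10 | 7.2 | 6.0 | 4.7 | 2.7 | 8.1 |
| 14 | 10.0 | 8.5 | 6.6 | 3.8 | 11.3 |

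Paired power for a 5-day delay runs from 0.17 (SD 14, r = 0.3) to 1.00 (SD 7, r = 0.9). In the same simulations the difference of the two site medians varies 1.3 to 2.0 times as much as the mean paired difference.

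**4. Coarse dates.** Protocol 9.1.1 has closure assessed daily or as often as possible at dressing changes; scheduled visits are Days 7, 14, 21, 28 and 42 and Month 2. In the worst case, with closure recorded only at scheduled visits (SD 8, 5-day delay), about 5 to 6 of 13 pairs tie, and the simple median of the paired differences is exactly 0 in about 60% of runs. Power falls to about 0.36 at r = 0.5 and 0.49 at r = 0.8. The estimator must therefore not be the simple median.

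**5. Mesh groups.** Thirteen subjects leave about 6 or 7 per group (the split is not given). The smallest two-sided signed-rank p is 2 × 0.5⁵ = 0.0625 with 5 pairs, so no exact 95% interval exists. With 6 pairs it is 0.031, and the interval spans the extremes.

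**The case against.** The best defence is that the endpoint is exploratory, SAP 3.7.1 limits all p-values to signal exploration, and section 3.7 asks for within-subject comparison only where appropriate. Marginal medians are legitimate description, and the SAP plans no unpaired test, so nothing invalid would be reported. That stands. The independent-sites figures above are only a yardstick for the value of pairing.

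A reader might go further than the documents allow in four ways.

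- *That time to closure is the only closure measure not at its ceiling.* SAP 2.5 documents a ceiling only for closure by Month 2, in the first 10 subjects. Nothing shows that percent re-epithelialization or confirmed closure at Days 14 to 42 is at a ceiling.
- *That slower SOMA healing is never examined within subject.* The paired t-tests on percent re-epithelialization in 3.7.2 do examine it, indirectly. What they lack is the scale of days.
- *That mesh groups are ignored.* Section 3.7 plans descriptive summaries by m+1 and m+2; 3.7.3.2 does not repeat this. The table shells are a separate document.
- *That the endpoint's origin is hidden.* Section 2.2.7 discloses it and points to 2.2.3. What remains is to carry the disclosure to where results are read.

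The point about coarse dates also stands. It limits what any paired summary can show and shapes the fix.

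**Conclusion.** The point holds in a limited form. Section 3.7.3.2 specifies two marginal medians and nothing that compares them, so the within-subject difference in days and its uncertainty will not be estimated. Neither the Month 2 co-primary (at most 3 discordant pairs, p no smaller than 0.25, if the 2.5 result is unchanged in the final data) nor the re-epithelialization tests supply that estimate.

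The size of the gain cannot be fixed from the documents. It rests on an assumed SD and on positive correlation between two matched sites on one patient, which is plausible but not reported. The widths in step 3 are illustrations. Recording closure only at scheduled visits would reduce the gain further. The consequence is lost information on an exploratory endpoint, so this is a worthwhile and cheap improvement that does not threaten the validity of the trial.

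**What to change.** In SAP 3.7.3.2, keep Kaplan-Meier as description and add:

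1. The within-subject difference in days to confirmed closure, SOMA minus AG, for all subjects: Hodges-Lehmann estimate with a signed-rank 95% confidence interval, using a method that allows for ties and zero differences.
2. The number of pairs with SOMA later, tied, and AG later.
3. A rule for failures: a site with no qualifying closure by Month 2 ranks later than any observed time, and a pair in which both sites fail counts as tied. If 2.5 stands, this affects at most 3 pairs. Even with 3 SOMA-only failures, 91 − 55 = 36 of the 91 pairwise averages (13 × 14/2, less the 10 × 11/2 that are unaffected) are indeterminate, under half, so the estimate exists. An interval limit may be open and should then be reported as open.
4. A listing of individual paired differences by m+1 and m+2 group, without an interval.

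State in the table title and the CSR, as 2.2.7 already does, that the endpoint was added after its results had been reported.

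Cost: a few lines of SAP text and one extra table from dates already derived. The downside is that the difference will be coarse if closure was mostly seen at scheduled visits, and the table should say so.

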3.8 Safety

The safety analysis, including adverse events (AEs), treatment-emergent adverse events (TEAEs), laboratory results, and vital signs, will be based on the safety population (SAF).

3.8.1 Adverse Events

An AE is any untoward medical occurrence in a patient or clinical study participant, temporally associated with the use of study treatment, whether or not considered related to the study treatment.

All adverse events (AEs) will be assessed and recorded before and after first placement of study product. Adverse events will be coded using the Medical Dictionary for Regulatory Activities (MedDRA), version 23.0. The number of TEAE/AEs, and the number of subjects reporting TEAE/AEs will be listed and summarized by body system, preferred term, severity, and relationship, and by relative autograft mesh ratio group at the SOMA Tx site (m+1 and m+2), cohort and treatment sites or "other"). All serious AEs (i.e., SAEs) will be summarized by relative autograft mesh ratio group at the SOMA Tx site (m+1 and m+2), cohort and location, and narratives will be created. The incidence of wound infection-related events will be listed and summarized overall by subject, by relative autograft mesh ratio group at the SOMA Tx site (m+1 and m+2), cohort, and treatment sites, and if applicable, by subject.

The focus of the AE data summaries will be on treatment-emergent adverse events (TEAE).

Treatment emergent AEs are defined as AEs for which the AE start date is on or after the start of

study drug administration date. For AEs with missing onset dates, the first day of study treatment will be used as the onset date.

If a subject has more than one TEAE coding to the same preferred term, the subject will be counted only once for that preferred term. Similarly, if a subject has more than one TEAE within a system organ class category, the subject will be counted only once in that system organ class category.

The following TEAEs will be summarized by frequency and percentage of subjects by SOC and PT and by cohort, by relative autograft mesh ratio group at the SOMA Tx site (m+1 and m+2), by treatment sites, if applicable, and all subjects:

- All TEAEs.
- TEAEs by SOC and PT.
- TEAEs by Relationship.
- TEAE by Maximum Severity.
- TEAEs by Relationship and Maximum Severity.
- TEAEs by Location.
- TEAEs Location and Relationship.
- TEAEs leading to Withdrawals by Relationship.
- Infection Assessment (Yes/No) at Study treatment Sites by Clinician.
- TEAEs of Special Interest (AESIs) by SOC and PT.
- Serious Treatment-Emergent Adverse Events (TEAEs) by SOC and PT.
- Serious TEAEs by Relationship.
- Serious TEAEs by Location.
- Serious TEAEs by Location and Relationship.
- Serious TEAEs of Special Interest by SOC and PT.

The listing of AEs with relative autograft mesh ratio group at the SOMA Tx site (m+1 and m+2), TEAE flag, location of the AE, SOC/PT/Verbatim Term, Outcome, Wound Infection Related, Relationship, Action Taken, and Serious etc. will be presented by subject.

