9.2.1. Adverse Events (AEs)

All AEs that occur after the subject has signed the study ICF will be collected for the duration of their participation. It is anticipated that each subject will participate in this study for up to 14 months: up to 2 weeks of screening followed by up to 12 months (\pm 4 weeks) of post-treatment observation. See [Appendix 4](#) for further description and information categorizing AEs.

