10.3. Statistical Analyses

The statistical analysis plan will be developed and finalized before database lock and will describe the participant populations to be included in the analyses, and procedures for accounting for missing, unused, and spurious data. This section is a summary of the planned statistical analyses of the primary and secondary endpoints.

For continuous variables, descriptive statistics will include the following: the number of patients reflected in the calculation (n), mean, median, standard deviation, minimum, and maximum.

For categorical or ordinal data, frequencies and percentages will be displayed for each category.

The definition of primary and secondary endpoints is described in [Section 4](#).

Safety assessments will include monitoring of AEs, vital signs, laboratory safety values, incidence of wound infection-related events, and immunologic responses to StrataGraft.

TEAE is defined as new or worsening AE after active Study Tx has been administered.

Safety assessments

1. Incidence of TEAE throughout study
2. Incidence of TEAE related to StrataGraft or Autografting procedure
3. Incidence of wound infection-related events at Study Tx sites
4. Clinically significant changes in vital signs throughout study compared to Baseline
5. Clinically significant changes in laboratory values between Baseline and Day 28

10.3.1. Advancement to Cohort 2

Following excision, a total of 20 subjects (Cohort 1) will be randomized into one of 2 groups:

- Group 1 subjects (n=10) will receive autograft (mesh ratio “m”, chosen per clinical judgment) compared to m+1:1 meshed autograft overlaid with StrataGraft
- Group 2 (n=10) will receive meshed autograft (mesh ratio “m”, per clinical judgment) compared to m+2:1 meshed autograft overlaid with StrataGraft, applied to wounds of 100 to 400 cm² in area.

Following completion of the Day 28 assessments, each subject will be determined to be a success or failure based upon the criteria below:

- % closed at Day 28, with success declared if the difference between paired wounds $\leq 10\%$, and
- Total score of Observer assessment of the POSAS at Day 28, with success declared if the difference between paired wounds $\leq 20\%$.

Group success will be declared if $\geq 80\%$ subjects are determined to have treatment success within that group. Only one of the 2 SOMA TxS, m+1 or m+2, will be determined to meet the *a priori* established criteria above and become the SOMA Tx in Cohort 2.

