3.1.1 Handling of Missing Data

No imputation for missing values will be conducted. All observed values (i.e., excluding missing values for visit) will be used for the analyses except for the second co-primary endpoint, missing data will be imputed as non-responder.

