3.1.2 Date/Time Derived Variable Conventions

Study Day 1 when Study Tx is applied will be considered as baseline for the endpoint calculations.

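### SAP 3.8.1 sets every missing AE onset to Day 1 without checking the end date, so an undated AE that ended before grafting would count as treatment-emergent

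*SAP*

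**What the plan says.** The SAP's test for a treatment-emergent event is a comparison of dates. Section 3.8.1 reads "Treatment emergent AEs are defined as AEs for which the AE start date is on or after the start of" study drug administration. The next sentence supplies a date where there is none: "For AEs with missing onset dates, the first day of study treatment will be used as the onset date". No condition is attached.

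The first day of treatment is fixed in SAP 3.1.2: "Study Day 1 when Study Tx is applied will be considered as baseline for the endpoint calculations". That section contains no other date convention.

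Events from before grafting are in the data by design. SAP 3.8.1 says "All adverse events (AEs) will be assessed and recorded before and after first placement of study product". Protocol 9.2.1 says "All AEs that occur after the subject has signed the study ICF will be collected for the duration of their participation", and describes participation as "up to 2 weeks of screening followed by up to 12 months" of follow-up. The Schedule of Activities marks AE assessment in the Day -14 to Day -1 column.

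Protocol 10.3 defines the term by timing relative to treatment: "TEAE is defined as new or worsening AE after active Study Tx has been administered". The SAP's list of departures from the protocol's statistical section (2.2.7) does not mention the TEAE definition.

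SAP 3.1.1 opens with a general statement, "No imputation for missing values will be conducted", and names the second co-primary endpoint as the only exception.

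**The concern.** Using Day 1 for an undated AE is a sound conservative choice when the event could have started after grafting. It stops being conservative and becomes wrong when the record already shows that the event was over before grafting. In that case the rule overrides known information, produces a record whose onset follows its end, and puts a pre-treatment event into the treatment-emergent tables.

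TEAE incidence is the first safety measure listed in SAP 2.2.4, and SAP 3.8.1 makes TEAEs the focus of its AE summaries. The flag feeds the tables by system organ class and preferred term, relationship, maximum severity, location and seriousness. With so few subjects, a single misclassified record is visible in a percentage.

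**Working it through.** The plan gives no figure to reproduce. The check applies the rule as written to test records and then works out the scale.

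**Inputs.** Day 1 is the day study treatment is applied (SAP 3.1.2). Pre-treatment days run from Day -14 to Day -1, with no Day 0 (Schedule of Activities). Thirteen subjects were randomized, all in Cohort 1 (SAP 2.1). The safety set is subjects who consented and received the investigational treatment (SAP 3.2.4); its size is not given. Each subject counts once per preferred term and once per system organ class (SAP 3.8.1).

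**Rule as written.** Onset = Day 1 if missing. TEAE = yes if onset is Day 1 or later.

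**Rule with an end-date condition.** The same, except that an AE with a missing onset and an end date before Day 1 keeps a missing onset and is not a TEAE.

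| Test record | As written | With end-date condition |
|---|---|---|
| Onset missing, ended Day -3 | Onset Day 1, TEAE, onset after end | Not a TEAE |
| Onset missing, ended Day 10 | Onset Day 1, TEAE | Onset Day 1, TEAE |
| Onset missing, ongoing | Onset Day 1, TEAE | Onset Day 1, TEAE |
| Onset Day -5, ended Day -3 | Not a TEAE | Not a TEAE |
| Onset Day 2, ended Day 9 | TEAE | TEAE |

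Only the first record changes. With no Day 0, an end date of Day -k lies k calendar days before Day 1. The imputed onset therefore follows the end by 3 days in the example, and by 1 to 14 days for end dates from Day -1 to Day -14.

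**Against the protocol definition.** An event that ended on Day -3 was not new after Day 1, and it could not worsen after it had resolved. It fails both parts of the definition in Protocol 10.3.

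**Scale.** Each affected AE adds one to the count of events. Its effect on a subject percentage depends on the row:

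- Overall row, assuming all 13 are in the safety set and the subject is not otherwise in the row: 1/13 = 7.7 percentage points.
- Same row, subject already counted there for another TEAE: 0.
- Row within a mesh-ratio group: group sizes are not given. Assumed sizes of 7, 6 and 5 give 1/7 = 14.3, 1/6 = 16.7 and 1/5 = 20.0 points, on the same conditions.

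The number of AEs with a missing onset and a pre-Day 1 end date is not in the documents. It may be zero.

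**The case against.** The strongest reply is that the trigger is narrow and the consequence small. A record must have an end date but no start date, and must fall within at most 14 days, under source data verification (Protocol Appendix 3). The by-subject AE listing carries the TEAE flag, so an oddity among 13 subjects could be spotted. The error hides no event. Causality assessment takes timing into account (Protocol Appendix 4), so an event resolved before grafting should be rated unrelated. Sites are randomized only after excision, so such an event cannot systematically favor either treatment. Enrollment stopped for business reasons and no further decision in the trial turns on this. All of that stands, and it is why the point is minor.

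It is also true that derivation rules sit in separate programming specifications (SAP section 5) that were not supplied, and an end-date check could be there. However, the SAP neither states nor refers to one, and Protocol 10.3 assigns the handling of missing data to the SAP.

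Several stronger readings are tempting but not supported:

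- **Partial dates.** A reader might infer that a start date with a known month before grafting is also moved to Day 1. The SAP speaks only of missing onset dates and does not say that a partial date counts as missing. This is an ambiguity, not a demonstrated misclassification.
- **Conflict with SAP 3.1.1.** The general no-imputation statement could be read as contradicting 3.8.1. It is framed around visit values and endpoints, and the specific AE rule can govern AE dates. What is missing is mainly a cross-reference.
- **Every safety table.** Not all output listed in 3.8.1 depends on onset date; the clinician's yes/no infection assessment at the study sites does not.
- **Burn events in general.** The rule does not sweep in the burn and its care. Only events after consent are collected, and expected features of the condition under study are not AEs unless more severe than expected (Protocol Appendix 4).

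**Conclusion.** The point holds in a narrow form. As written, SAP 3.8.1 would classify an undated AE known to have ended before Day 1 as treatment-emergent, contrary to the protocol's own definition, and no other section supplied corrects it. This is a stated rule that gives a wrong answer for an identifiable type of record, not merely a missing detail.

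The direction is certain: TEAEs can only be over-counted. The size is not. The figure of 7.7 points is an upper limit per affected subject for an overall row and rests on the two conditions given with the calculation. For undated AEs that are ongoing or ended on or after Day 1, the existing rule is appropriate and should stay.

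**What to change.** In SAP 3.8.1, impute Day 1 for a missing onset only when the AE end date is missing or falls on or after Day 1. Otherwise classify the AE as pre-treatment and leave its onset missing.

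Two clarifications can go in with it: state that a partial onset date is classified by its known parts, and add a cross-reference in SAP 3.1.1 to the AE-date rule.

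The cost is a few sentences of SAP text and one condition in the TEAE flag. The downside is that TEAE counts become slightly less worst-case, because classification would then rely on the recorded end date being correct.
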